### 16.2.3 Best Overall Response, Disease Control Rate and Duration of Response

The parameters described in this section will be based on both IRC (radiologist) and investigator assessment as recorded in the “Assessment of Disease Based on Imaging” eCRF page. The BOR summary will also be produced based on the IRC clinical assessment.

The **BOR** for each subject is defined as the best result obtained among all tumor assessments from the randomization until documented disease progression. The overall response will be based on imaging, classified according to RECIST version 1.1 criteria (unconfirmed response).

The best possible overall response can be CR, PR, SD and PD, non-CR/non-PD, NE. If a subject has a missing baseline tumor assessment and/or no tumor assessment on-treatment, BOR will be Not Evaluable (NE). In the case the single response is SD, SD must have been assessed no less than 6 weeks (at least 42 days) after randomization, otherwise the best response will be NE.

The BOR rate (also referred as Objective Response Rate) is defined as the number of subjects, whom BOR was either Complete Response (CR) or Partial Response (PR), relative to the number of subjects belonging to the trial set of interest.

The **DCR** will also be based on imaging and classified according to RECIST version 1.1 criteria. The DCR is defined as the number of subjects whose BOR is either CR, PR or SD, divided by the number of subjects belonging to the trial set of interest.

The DOR will be determined for subjects whose BOR was either CR or PR. It is defined as the time from the first assessment of CR or PR until the event defining PFS time (see section 16.1.1) and expressed in weeks. The subjects with no event will be censored to the last tumor assessment data available before cut-off date or randomization date whatever comes later.

The following information will be summarized, by treatment group and overall:

- BOR per type of BOR (CR, PR, SD, PD, non-CR/non-PD and NE),
- BOR rate,
- DOR,
- DCR.

BOR rate and DCR will be presented with the corresponding two-sided 95% exact confidence interval based on the Clopper-Pearson method.

The odds ratio adjusted by randomization strata with associated 95% confidence interval will also be presented.

Subgroup analyses will comprise univariable unstratified analyses considering the subgroups as defined in Section 10. For each subgroup, odds ratio and p-value for the interaction test will be provided. In addition, the response rate with 95% exact confidence intervals using the Clopper-Pearson method will be computed.

To explore the treatment effect on the BOR when adjusted for exploratory variables of potential prognostic values, a multivariable analysis will also be conducted (the potential baseline prognostic factors variables used for this analysis will be the subgroup variables as defined in Section 10.2). A stepwise selection procedure will serve to identify explanatory variables of potential prognostic values additional to the randomization strata (as documented in the eCRF) which will be included in all models during the selection procedure. The level of significance for an explanatory variable to enter the model will be set to 0.15 and the significance level for removing will be set to 0.40. If there is a treatment by covariate interaction present in any of the covariates including in the model, the corresponding parameter will not be considered for the stepwise analysis.

For each covariate kept in the model, the p-value, the odds-ratio and the corresponding 95% CI will be provided. An odds-ratio  $> 1$  will indicate increased chance of response when a binary covariate takes the value 1, and increased chance of response for higher values of continuous covariates.

The listing of tumor assessments per time points (including e.g., type of lesion, imaging date, lesion description (site, type, size/status, assessment method), sum of diameter of TLs and overall response per timepoint) will also be provided based on data recorded on the “Tumor assessment - Target Lesions”, “Tumor assessment – Non-Target Lesions”, “Tumor assessment - New Lesions” and “Sum of diameters” eCRF pages.

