Tumors (RECIST) version 1.1. The baseline tumor assessment is to be performed during the screening period within 28 days before the start of trial treatment. Computed tomography (CT) or magnetic resonance imaging (MRI) with contrast enhancement is recommended for tumor assessment. Subsequent tumor response evaluations will be assessed every 6 weeks (± 3 days) starting from the first dose of trial treatment until occurrence of PD regardless of any cycle delay. If treatment is discontinued for reasons other than PD, subjects will continue to have tumor assessments until either PD, the start of a new antitumor treatment, death, the termination of the trial, or loss of follow up, whichever comes first. If symptoms are suggestive of PD, subjects will be evaluated by imaging studies thereafter for documentation and confirmation of the tumor responses.

All subjects in Arm A and B will be followed up continuously for safety evaluations according to schedule of assessments in Table 1.1 starting from date of first signature of informed consent. A Safety Follow-up visit will be performed 30 days (\pm 3 days) after the last dose of trial treatment or immediately before starting any new antitumor treatment. During the treatment period, additional safety evaluations will be on a weekly basis (Arm A only) for physical examination, vital signs, documentation of adverse events and concomitant medications, and also at the start of each cycle (for both arms) Eastern Cooperative Oncology Group (ECOG) performance status, electrocardiogram (ECG), hematology, biochemistry and urinalysis. Survival data will be collected every 3 months after the end of efficacy assessment (EOEA) visit until either death, loss of follow up, or the termination of the trial, whichever comes first.

The trial will be terminated when the last subject has discontinued the trial treatment or OS cut-off, whichever is later. After OS cut-off and before the trial termination, only SAEs during treatment and at the EOEA visit will be reported, following the usual reporting procedure.

Information collected in the EOEA forms will be limited to data on date of trial treatment completion, date of last treatment, subject status at end of trial, reason for discontinuation, disease progression (yes/no). From alive, but trial-treatment-discontinued subjects, no tumor response data, anti-cancer treatment and survival information will be collected.

Planned number of subjects: 240 subjects.

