Tumor assessment: Tumor assessment will be performed according to RECIST version 1.1. The baseline tumor assessment is to be performed during the screening period within 28 days before the start of trial treatment. Computed tomography (CT) or magnetic resonance imaging (MRI) with contrast enhancement is recommended for tumor assessment. Subsequent tumor response evaluations will be assessed every 6 weeks (± 3 days) starting from the randomization day until occurrence of PD regardless of any cycle delay. If treatment is discontinued for reasons other than PD, subjects will continue to have tumor assessments until either PD, the start of a new antitumor treatment, death, the termination of the trial, or loss of follow up, whichever comes first. If symptoms are suggestive of PD, subjects will be evaluated by imaging studies thereafter for documentation and confirmation of the tumor responses. The details of documentation of tumor assessment is described in Section 7.3.1.

Safety follow-up period: All subjects in Arm A and B will be followed up continuously for safety evaluations according to schedule of assessments in Table 1.1 starting from date of first signature of informed consent. A Safety Follow-up visit will be performed 30 days (± 3 days) after the last dose of trial treatment or immediately before starting any new antitumor treatment. During the treatment period, additional safety evaluations will be on a weekly basis (Arm A only) for physical examination, vital signs, documentation of AEs and concomitant medications, and also at the start of each cycle (for both arms) for ECOG performance status, ECG, hematology, biochemistry and urinalysis. Survival data and any information on new antitumor treatments will be collected every 3 months after the EOEA visit until either death, loss of follow up, or the termination of the trial, whichever comes first.

Primary and secondary endpoints: The primary endpoint of this trial is PFS time, as assessed by an IRC. Secondary endpoints include PFS time, as assessed by the Investigator, OS time, BOR rate, DCR, duration of response, and safety (see Section 8).

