6.3 Assignment to Treatment Arms

All subjects will be assigned a subject number by the Investigator at the screening visit. Subjects who enter the trial will retain this number throughout the trial.

Randomization will occur on Day 1, the same day the trial treatment is initiated, but before the first dose of trial treatment. For subjects randomized to Arm A, prophylactic administration of a tetracycline is recommended, starting 1 day before the administration of the first dose of cetuximab. In this case, trial treatment will be initiated 1 day after randomization which will be performed on Day -1. Once an eligible subject has signed the informed consent form (ICF), the center will use an IWRS and receive instructions regarding treatment assignment. Allocation to the 2 treatment arms will be in a ratio of 2:1.

Randomization will be stratified according to ECOG (0 versus 1) and the primary tumor site (oral cavity versus hypopharynx versus others) to balance these factors across the treatment arms and thus improve comparability of the results.

The randomization list will be generated by the designated contract research organization under the responsibility of the Sponsor's trial statistician. Specific details will be provided in a separate Manual of Operations.

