7.3.2 Criteria for Tumor Response Evaluation

Tumor response evaluation will be performed according to RECIST version 1.1 (see Appendix I) by using CT or MRI and other modalities at a 6-week interval starting from the first dose of trial treatment. In the case of symptoms suggesting progression, subjects should be evaluated by imaging thereafter for documentation and confirmation of the tumor responses.

Evaluation of lesions should be based on images obtained by either CT or MRI. The same method of assessment and the same technique should be used to characterize each identified and reported lesion at baseline and during the trial. If a chest X-ray indicates metastatic disease while the subject is enrolled in this trial, a CT of the chest is required for confirmation. All assessments should be provided by the same physician or radiologist if possible during the trial.

Evaluation criteria for possible combination of tumor responses (e.g., target lesion, nontarget lesion, new lesion, and overall response) are provided in Appendix I.

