### Methodology:

This is an open-label, randomized, parallel-group trial. At the end of a 28-day screening period, all eligible subjects will be randomly assigned into treatment Arm A or B in a 2:1 ratio. Subjects in Arm A will receive a maximum of 6 cycles of chemotherapy (cisplatin plus 5-FU) and cetuximab weekly in the absence of progressive disease (PD), as assessed by the Investigator, and unacceptable toxicity. After 6 cycles of treatment, subjects who derive clinical benefit will continue treatment with cetuximab as monotherapy until either PD or unacceptable toxicity. Subjects in Arm B will receive the same chemotherapy regimen as Arm A alone for a maximum of 6 cycles in the absence of PD and unacceptable toxicity.

Tumor assessment will be performed according to Response Evaluation Criteria in Solid Tumors (RECIST) version 1.1. The baseline tumor assessment is to be performed during the screening period within 28 days before the start of trial treatment. Computed tomography (CT) or magnetic resonance imaging (MRI) with contrast enhancement is recommended for tumor assessment. Subsequent tumor response evaluations will be assessed every 6 weeks ( $\pm$  3 days) starting from the randomization day until occurrence of PD regardless of any cycle delay. If treatment is discontinued for reasons other than PD, subjects will continue to have tumor assessments until either PD, the start of a new antitumor treatment, death, the termination of the trial, or loss of follow up, whichever comes first. If symptoms are suggestive of PD, subjects will be evaluated by imaging studies thereafter for documentation and confirmation of the tumor responses.

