- Events: Radiological PD based on existing lesions (progressive disease reported for target and/or non-target lesions) / Radiological PD based on new lesions (new lesion(s) is/are reported) / Radiological PD based on existing and new lesions (both progressive disease reported for target and/or non-target lesions and new lesion(s) are reported) / Death within 60 days
- Censoring: Death not within 60 days / Censored at randomization / Lost to follow-up or withdraw consent / Due to data cut-off

Subjects will be considered as “censored at randomization” in case they have no tumor assessment at baseline and no tumor assessment after start of treatment and no radiological PD or death.

They will be considered as censored due to “Lost to follow-up/withdraw consent” in case they have no PD or death before they are lost to follow-up/withdraw consent.

They will be considered as censored “due to cut-off” in case they have no PD or death before the trial data cut-off.

A listing will display information on event and censoring including the following:

- Subject identification number,
- Treatment arm
- Randomization Date
- Last tumor assessment date before cut-off date
- Death date
- Progression date (IRC)
- PFS (IRC): Censoring Flag (Yes/No)/ Description of the Event/Censoring/ PFS (months)

A scatter plot will be produced to compare planned (y-axis) and actual (x-axis) relative day of tumor assessments by treatment arm (2 colors will be used to clearly identify treatment groups). The planned day for EOEA visit will be assigned as the planned day for the last available efficacy assessment visit.

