### 16.1.2 PFS Sensitivity Analyses

To assess the robustness of the primary analysis, the following analyses can be conducted:

- Per-protocol analysis: the same analysis as described above Section 16.1.1 will be repeated on PP analysis set only if PP analysis set includes less than 90% of the ITT analysis set.
- The same analysis as described above Section 16.1.1 will be repeated using results of the *clinical* review from IRC, corresponding listing will also be produced.
- The same analysis as described above Section 16.1.1 will be repeated considering all death as event.
- The same analysis as described above Section 16.1.1 will be repeated considering all death and start of new anti-cancer treatment as event.
- To address the bias due to different times of assessment of disease progression caused by different treatment schedules, the same analysis as described above Section 16.1.1 will be repeated considering date of planned imaging visits instead of date of actual imaging visits. If an event is observed between two planned visits, it will be assigned to the previous one. The planned day for EOEA visit will be assigned as the planned day for the last available efficacy assessment visit.
- The same analysis as described above Section 16.1.1 will be repeated excluding subjects who met the inclusion criteria 3 as defined in protocol version 1.0 (17 November 2014) but who do not meet the updated inclusion criteria 3 as defined in protocol version 2.0 (20 April 2016). Please refer to [Appendix 2](#) for the details for inclusion criteria 3.
- The same analysis as described above Section 16.1.1 will be repeated based on the stratification factors based on eCRF data instead of IWRS data.

Results of PFS primary and sensitivity analyses (hazard ratio and 95%CI) will be displayed using a forest plot.

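### The 42-day minimum for a lone stable disease result ignores the trial's own ±3-day scan window, so some on-schedule scans become not evaluable and count against the disease control rate

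*SAP*

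**What the plan says.** SAP 16.2.3 defines best overall response (BOR) over all assessments from randomization to progression and adds a time condition for SD: "In the case the single response is SD, SD must have been assessed no less than 6 weeks (at least 42 days) after randomization". If the condition is not met, BOR is NE. No window tolerance is given, and the SAP does not say what counts as a single response.

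DCR is the share of subjects whose BOR is CR, PR or SD, over everyone in the analysis set (protocol 8.3.2, SAP 16.2.3). SAP 16.2 makes that set ITT. NE therefore stays in the denominator and outside the numerator.

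On scan timing the documents use two anchors:

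- Randomization. Protocol 5.1: "Subsequent tumor response evaluations will be assessed every 6 weeks (± 3 days) starting from the randomization day". SAP section 6, Methodology, agrees: "starting from the randomization day until occurrence of PD regardless of any cycle delay".
- First dose. Protocol synopsis: "starting from the first dose of trial treatment until occurrence of PD regardless of any cycle delay". Protocol 7.3.2: "at a 6-week interval starting from the first dose of trial treatment".

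The anchors usually coincide, because protocol 6.3 places randomization and first dose on the same day. The exception is when tetracycline prophylaxis is planned: "trial treatment will be initiated 1 day after randomization which will be performed on Day -1".

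The SAP already pays attention to scan timing for PFS. Section 16.1.1 says "A scatter plot will be produced to compare planned (y-axis) and actual (x-axis) relative day of tumor assessments by treatment arm", and section 16.1.2 repeats the primary analysis "considering date of planned imaging visits instead of date of actual imaging visits". Section 16.2.3 has nothing comparable for the SD minimum.

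**The concern.** The floor sits at the centre of the permitted window for the first scan. Two subjects with the same tumor finding, both scanned on schedule, can receive different outcomes: SD and disease control if the scan fell on day 42, NE and no disease control if it fell on day 40. The difference comes from the booking date and carries no information about the disease.

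The undefined term adds a second problem. *Single response* could mean the only post-baseline assessment or the only result that is not PD. For a subject with SD on day 40 and PD at the next scan, the first reading leaves BOR as SD and the second makes it NE. Appendix I of the protocol, in its section on best overall response, would call it PD. Two programmers could therefore produce different BOR tables from the same data.

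At stake are DCR, its strata-adjusted odds ratio, and the SD, NE and PD rows of the BOR table, for both IRC and investigator assessments.

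**Working it through.** **Inputs.** SD floor: 42 days after randomization (SAP 16.2.3). Scan interval and window: 6 weeks ±3 days (protocol 5.1, SAP section 6). Gap from randomization to first dose: 0 days as a rule, 1 day when randomization is on Day -1 (protocol 6.3). General duration rule: stop date minus start date plus 1, unless otherwise specified (SAP section 11). Planned size: 240 at 2:1 (protocol 5.1).

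**The plan's own figure.** 6 × 7 = 42 days, so the floor is exactly 6 weeks.

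**Window against floor.** First-scan window in days after randomization = 42 + gap ± 3, where the gap counts only if scans run from first dose. A day fails if its count is below 42.

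| Scan anchor | Day count | Window (days after randomization) | Days that fail | Share |
|---|---|---|---|---|
| Randomization, or first dose on the same day | plain difference | 39–45 | 39, 40, 41 | 3/7 |
| Randomization, or first dose on the same day | difference + 1 | 39–45 | 39, 40 | 2/7 |
| First dose, 1 day after randomization | plain difference | 40–46 | 40, 41 | 2/7 |
| First dose, 1 day after randomization | difference + 1 | 40–46 | 40 | 1/7 |

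The first row fits the text best: the SAP anchors scans at randomization, and a floor stated as a number of days after randomization reads as a plain difference. The other rows narrow the gap but do not close it.

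**Who is affected.** The rule bites only if no later qualifying SD, PR or CR is recorded. A subject with SD on day 40 and SD again at the week-12 scan is SD under any reading.

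**Weight of one subject.** Planned ITT: 240 × 2/3 = 160 in Arm A and 240 × 1/3 = 80 in Arm B. One reclassified subject moves DCR by 1/160 = 0.625 points or 1/80 = 1.25 points. A 5-point change takes 0.05 × 160 = 8 subjects in Arm A or 0.05 × 80 = 4 in Arm B.

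**Illustration only.** Loss in DCR = share of subjects with a lone SD × share of those scanned on a failing day. The documents give neither share. Assuming 5% to 20% for the first, and scans spread evenly over the window for the second (1/7 to 3/7), the loss runs from 0.05 × 1/7 = 0.7 points to 0.20 × 3/7 = 8.6 points. The conclusion does not rest on this range.

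**Check of the fix.** With a floor of 42 − 3 = 39 days, the earliest in-window scan is day 39 or day 40 depending on the anchor. No window day fails in any of the four rows.

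**The case against.** The best defence is that the two rules do different jobs. A visit window says when a scan complies; an SD minimum says how long disease must hold before it counts as controlled. Nothing in the documents promises that every compliant scan will qualify. Appendix I leaves the minimum to the trial and suggests 6 to 8 weeks or more as a general guide. A 42-day floor fits that, and a 39-day floor falls just short of it. Appendix I also treats a subject lost after an SD that misses the minimum as inevaluable, which is the SAP's NE.

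Much of this stands. A reader might infer that the 6-week minimum, or the NE category, departs from Appendix I; neither does. What the defence does not explain is why disease control should turn on which compliant day was booked, when the SAP re-runs PFS on planned dates to deal with scan timing.

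Three further inferences would go too far:

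- *That 3 of 7 days applies throughout.* It is the largest case. The general plus-one rule, or a first-dose anchor with a one-day gap, gives 2 of 7; both together give 1 of 7.
- *That the arms are treated differently.* Prophylaxis is recommended for Arm A, which suggests a one-day gap there only. But note 6 to Table 1.1 ties Day -1 randomization to the investigator's willingness to give prophylaxis, which is settled before the arm is known. The documents do not give the dosing day for Arm B subjects randomized on Day -1, so no arm-specific count can be made.
- *That DCR will be materially lowered.* A later qualifying assessment rescues a subject, and the spread of scan days is unknown.

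**Conclusion.** The mismatch is real and minor. Under every reading of anchor and day count, at least one on-schedule day for the first scan falls below the SD floor; under the reading the text best supports, three days do. A lone SD on such a day becomes NE and counts as a DCR failure on the ITT set.

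The number of subjects affected cannot be derived from the documents. It depends on how scan days are spread, on how many subjects have no later qualifying result, and on what *single response* means. PFS, OS, the CR+PR rate and duration of response are unaffected. Protocol 8.5.3 makes the secondary analyses exploratory. The planned scan-day plot and the dated listing of tumor assessments will allow the affected subjects to be counted.

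**What to change.** In SAP 16.2.3, for both IRC and investigator assessments:

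1. Set the SD minimum at 39 days after randomization (6 weeks less the 3-day window) and state that days are a plain date difference.
2. Report DCR with the strict 42-day floor as a sensitivity row.
3. Say whether *single response* means the only assessment or the only result that is not PD.
4. Class SD before the minimum followed by PD as PD, as Appendix I does. If such subjects would now be NE, they move between the NE and PD rows and DCR is unchanged. If they would now be SD, DCR falls. The edit should say which applies.

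The cost is a few lines of text and one extra table row; no new data are needed, since scan dates are already recorded and listed. The 39-day floor works under either scan anchor, so this edit need not wait for the two anchors to be reconciled. The downside is that a few subjects count as SD at 39 to 41 days, just under the general 6 to 8 weeks in Appendix I; the 42-day row shows how much that matters.

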The best OR is the best response recorded from the start of the trial treatment until the end of treatment taking into account any requirement for confirmation. On occasion, a response may not be documented until after the end of therapy, so protocols should be clear if post-treatment assessments are to be considered in determination of best OR. Protocols must specify how any new therapy introduced before progression will affect best response designation. The subject's best OR assignment will depend on the findings of both target and non-target disease and will also take into consideration the appearance of new lesions. Furthermore, depending on the nature of the trial and the protocol requirements, it may also require confirmatory measurement. Specifically, in non-randomized trials where response is the primary endpoint, confirmation of PR or CR is needed to deem either one the 'best OR'.

The best OR is determined once all the data for the subject is known. Best response determination in trials where confirmation of complete or partial response IS NOT required: Best response in these trials is defined as the best response across all time points (for example, a subject who has SD at first assessment, PR at second assessment, and PD on last assessment has a best OR of PR). When SD is believed to be best response, it must also meet the protocol specified minimum time from baseline. If the minimum time is not met when SD is otherwise the best time point response, the subject's best response depends on the subsequent assessments. For example, a subject who has SD at first assessment, PD at second and does not meet minimum duration for SD, will have a best response of PD. The same subject lost to follow-up after the first SD assessment would be considered inevaluable.

Target Lesions	Non-target Lesions	New Lesions	Overall Response
CR	CR	No	CR
CR	Non-CR/non-PD	No	PR
CR	Not Evaluated	No	PR
PR	Non-PD or not all evaluated	No	PR
SD	Non-PD or not all evaluated	No	SD
	Non-PD		
Not all evaluated	evaluated		Not Evaluable
PD	Any	Yes or No	PD
Any	PD	Yes or No	PD
Any	Any	Yes	PD

CR = complete response; PR = partial response; PD = progressive disease; and SD = stable disease. See text for more details.

Note:

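### The SAP's minimum-time rule for stable disease has no PD outcome, so an early SD followed by progression is classified differently from protocol Appendix I

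*SAP*

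**What the plan says.** SAP 16.2.3 defines BOR as the "best result obtained among all tumor assessments from the randomization until documented disease progression". It then adds one condition on SD: "In the case the single response is SD, SD must have been assessed no less than 6 weeks (at least 42 days) after randomization". A subject who misses this minimum is classed as NE. The DCR is built directly on BOR: "The DCR is defined as the number of subjects whose BOR is either CR, PR or SD", divided by the size of the analysis set. BOR and DCR are derived from both the IRC radiology read and the Investigator's assessment.

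Protocol 7.3.2 points to Appendix I for the response criteria. Appendix I places the minimum on every SD that would become the best response: "When SD is believed to be best response, it must also meet the protocol specified minimum time from baseline". It then works through two cases. The first is a subject with "SD at first assessment, PD at second and does not meet minimum duration for SD, will have a best response of PD". The second is the same subject lost to follow-up after the first SD, who is inevaluable.

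Appendix I leaves the length of the minimum to the trial protocol and mentions 6 to 8 weeks as usual. The protocol body gives no figure, and the DCR definition in protocol 8.3.2 has no minimum. The 42 days appear only in the SAP.

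Imaging is every 6 weeks ± 3 days in both arms (protocol 5.1), with extra imaging when needed: "If symptoms are suggestive of PD, subjects will be evaluated by imaging studies thereafter".

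**The concern.** The SAP reproduces the second Appendix I case (early SD, nothing later, NE) but not the first (early SD, then PD). Because its condition is tied to a single response, a subject with two assessments falls outside it, and the general best-result rule then returns SD.

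The literal result runs backwards. An SD at Day 21 with no later scan is not disease control, but the same SD followed by documented progression is, so evidence of progression improves the classification. A looser reading of the condition sends that subject to NE instead, which lists a documented progressor as not evaluable.

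Two programmers could therefore derive different DCRs from the same sentence, and neither result would match Appendix I. What is at stake is the SD, PD and NE rows of the BOR table, the DCR with its exact confidence interval, and any stratum-adjusted odds ratio computed for DCR.

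**Working it through.** **Inputs.** Minimum for SD: 6 weeks (SAP 16.2.3). Week length: 7 days (SAP 11). Planned size: 240 subjects, randomized 2:1 (protocol 5.1). Scan window: ± 3 days (protocol 5.1).

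**The plan's own figure.** 6 × 7 = 42 days, as the SAP states.

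**The rules side by side.** Days are counted from randomization. The Appendix I column uses the SAP's 42 days.

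| Assessments | SAP, literal | SAP, if SD is the only non-PD response | Appendix I |
|---|---|---|---|
| SD Day 21, nothing later | NE | NE | NE |
| SD Day 21, PD Day 42 | SD | NE | PD |
| SD Day 40, PD Day 84 | SD | NE | PD |
| SD Day 42, PD Day 84 | SD | SD | SD |
| SD Day 40, SD Day 82, PD Day 126 | SD | SD | SD |
| SD Day 40, PR Day 82 | PR | PR | PR |

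The rules part only where an SD below the minimum is followed directly by PD. There the literal SAP wording always gives the higher DCR. The looser reading leaves DCR as under Appendix I and changes only the split between NE and PD.

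**Effect per subject on the literal reading.** Arm A: 240 × 2/3 = 160, and 1/160 = 0.625 percentage points. Arm B: 240 × 1/3 = 80, and 1/80 = 1.25 percentage points.

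**The scan window.** 42 − 3 = 39 and 42 + 3 = 45, so an on-schedule first scan can fall on Days 39 to 41, below the 42-day minimum. The third row of the table can therefore arise with no unscheduled scan, in a subject who was stable at the first planned assessment.

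**Why the window matters for the fix (illustration, assumptions mine).** Take exponential PFS with the EXTREME medians cited in protocol 3.7.2 (5.6 and 3.3 months), 30.4375 days per month, and scans at Days 42 and 84. The share progressing between the two scans is S(42) − S(84), with S(t) = 0.5^(t / (median × 30.4375)).

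- Arm A: 0.843 − 0.711 = 0.132. Arm B: 0.748 − 0.560 = 0.188.
- Low case, 5% of first scans before Day 42 and half of those SD: 0.132 × 0.05 × 0.5 = 0.3 points (A); 0.188 × 0.05 × 0.5 = 0.5 points (B).
- Upper bound, first scans spread evenly over the 7-day window (3/7 on Days 39 to 41) and all SD: 0.132 × 3/7 = 5.7 points (A); 0.188 × 3/7 = 8.1 points (B).

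These are the amounts by which a strict 42-day rule with no window allowance would lower DCR. The shares of early scans and of SD among them are not in the documents.

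**The case against.** The strongest reply is that this is loose wording rather than a wrong rule. SAP 16.2.3 also says that response is classified by RECIST 1.1, and protocol 7.3.2 adopts Appendix I, so a programmer might assign PD anyway. Appendix I is generic RECIST text, and its PD outcome applies only when a protocol-specified minimum is missed, which the protocol body does not specify. The conflict therefore appears only after the SAP's 42 days are carried into Appendix I, and the SAP's statement in section 9 that nothing changed adds little weight.

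Much of this stands, and it limits the claim. It does not remove it. The SAP's explicit sentence offers SD or NE for this sequence and never PD, so PD would have to come from a general reference that the specific sentence overrides.

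Two stronger inferences should be resisted.

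- A reader might conclude that DCR is overstated as a matter of fact. That follows only on the literal reading, and only if such subjects occur.
- A reader might conclude that the error favours Arm A, because cetuximab subjects attend weekly and so might be scanned early more often. The documents do not support this. Imaging is 6-weekly in both arms, the weekly visit in protocol 7.1.2 includes no imaging, and a symptom-driven scan could as well show PD. Under the window mechanism, the illustration above shows the larger shift in Arm B.

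It is also fair to say that the consequence is small. Protocol 8.5.3 makes the secondary analyses exploratory, no hypothesis test is planned, all BOR categories are tabulated, and responses are listed by time point.

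**Conclusion.** The point holds as a departure of SAP 16.2.3 from Appendix I for one sequence: an SD below the minimum followed directly by PD. The SAP gives SD (literal reading) or NE (looser reading); Appendix I gives PD. On the literal reading each such subject adds 0.625 points to DCR in Arm A or 1.25 points in Arm B, assuming the planned 160 and 80 subjects. The comparison rests on the SAP's own 42 days. The number of such subjects and the direction of any between-arm effect cannot be derived from the documents. PFS, OS, the CR+PR rate and duration of response are unaffected. Severity is low, because DCR is a secondary, exploratory endpoint.

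**What to change.** In SAP 16.2.3, replace the single-response condition with a rule for any SD that would otherwise be the BOR:

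- SD stands if at least one SD assessment meets the minimum time.
- If none does and the next evaluable assessment is PD, BOR = PD.
- If none does and there is no later evaluable assessment, BOR = NE.

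Align the minimum with the scan window, that is 42 − 3 = 39 days after randomization, so that an on-schedule first scan on Days 39 to 41 meets it. Without this allowance, a subject stable at an on-schedule Day 40 scan and progressing at Day 84 would become PD. Apply the rule to both IRC and Investigator BOR and DCR.

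The cost is a sentence or two in the SAP and one derivation. DCR may come out slightly lower than under the literal wording. The window allowance works the other way for a lone SD on Days 39 to 41, which the present text makes NE.
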